- ^g For women of childbearing potential: A serum beta-HCG pregnancy test will be performed at Screening and urine beta HCG will be performed either on the first day of each treatment period or the day before the first day of each treatment period at discretion of Investigator. In either case, the results must be negative prior to dosing study participants.
- ^h Female study participants of non-childbearing potential to confirm postmenopausal status.
- ⁱ Virus serology (HIV-1/2Ab, HBsAg, and HCV-Ab) only at Screening.
- ^j At the Screening Visit, "Baseline/Screening" version of the C-SSRS will be completed. At all other visits, "Since Last Visit" version of the C-SSRS will be completed.
- ^k Vital signs will be taken in a supine/standing position at Screening, and in a supine position at all other assessments.
- ^l NeuroCart assessments in Part B consist of the following tests: Body Sway, VAS mood & alertness (Bond & Lader), VAS feeling high, internal- and external perception (Bowdle), SEM, and Smooth Pursuit Eye Movements.
- ^m PD training session for all study participants. Training session will be performed at Screening or during a separate visit. Baseline PD assessment will be collected as a duplicate at D1 predose. Final Baseline score will be averaged (from duplicate values).
- ⁿ D1: CBD 10mg/kg SD; D15 (optional): CBD dose to be defined (within 5 and 20mg/kg SD)
- ^o CBD PK sampling will occur at 0, 0.25, 0.5, 1, 1.5, 2, 3, 4, 6, 8, 12 and 24 hours postdose.

Table 1-6: Assessment schedule Part B: Treatment Period 2

Study Period	Treatment Period 2 ^{a b}							
Study day	D -1	D1	D2	D3	D4	D5	D6	D7/D8
Adverse events	X	X	X	X	X	X	X	X
Psychiatric and mental status		X	X	X	X	X	X	X
Previous/concomitant med	X	X	X	X	X	X	X	X
Arrival at clinic	X							
Urine drug screen/ breath alcohol test ^l	X							
Urine sampling (blank aliquot) ^c	X							
Pregnancy test ^d	X							
Hem/chem/urine ^c	X	X			X			X
Neurocart								
C-SSRS ^e		X						X ^f
Brief physical examination		X			X			X ^f
Supine vital signs (BP, RR, HR, T) ^g		X			X	X	X	X ^f
Triplicate 12-lead ECG ^g		X			X	X	X	X ^f
PSL administration ^h		X	X	X	X	X	X	X
PSL PK trough sampling ^{c i}		X	X	X	X	X	X	X
NeuroCart ^j	X					X		
Urine sampling (blank aliquot) ^c	X							
Sample collection for exploratory genotype analysis ^c	X							
Start/stop urine collection						X ^k		
Discharge								X ^f

Table 1-6: Assessment schedule Part B: Treatment Period 2

Study Period	Treatment Period 2 ^{a b}							

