Study day	D -1	D1	D2	D3	D4	D5	D6	D7/D8

AE=adverse event; BID=twice daily; BP=blood pressure; C-SSRS=Columbia-Suicide Severity Rating Scale; D=Day; ECG=electrocardiogram; h=hour; HR=heart rate; PK=pharmacokinetic; PSL=Padsevonil; RR=respiratory rate; T=body temperature; SEM=Saccadic Eye Movements; VAS=Visual Analog Scale

^a For study participants that begin Part B in Treatment Period 2, Screening assessments will be performed according to the Screening assessments described in Table 1-5.

^b A washout of at least 6 days will occur at the end of Treatment Period 2 prior to Treatment Period 3 in Part B.

^c Prior to IMP administration.

^d For women of childbearing potential: A urine beta HCG will be performed either on the first day of the treatment period or the day before the first day of the treatment period at discretion of Investigator. The result must be negative prior to dosing study participants.

^e “Since Last Visit” version of the C-SSRS will be completed.

^f In Treatment Period 2, on Day 9 only.

^g Prior to and 2.5 hours after morning IMP administration.

^h D1: PSL 100mg BID; D2: PSL 200mg BID; D3: PSL 200mg BID; D4: PSL 200mg BID; D5: PSL 200mg AM; D5: PSL 100mg PM; D6: PSL 100mg BID; D7: PSL 100mg BID

ⁱ Blood samples for measurement of plasma concentration of PSL will be obtained at the following times: predose (within 5 minutes of dosing), and at Day 5 (PK day) postdose at 0.25h, 0.5h, 1h, 1.5h, 2h, 3h, 4h, 6h, 8h, and 12h postdose.

^j NeuroCart assessments in Part B consist of the following tests: Body Sway, VAS mood & alertness (Bond & Lader), VAS feeling high, internal- and external perception (Bowdle), SEM, and Smooth Pursuit Eye Movements. NeuroCarts assessments are taken twice at least 30 minutes prior to dosing and singlicate postdose at 30 minutes, 1, 2, 3, 4, 5, 6, 8, and 10 hours.

^k Urine collection for additional PK analysis will be collected for 12-hours post-morning dose on Day 5.

Table 1-7: Assessment schedule Part B: Treatment Period 3

Study Period	Treatment Period 3 ^a																
Study day	D-1	D1	D2	D3	D4	D5	D6	D7	D8	D9	D10	D11	D12	D13	D14	D15	D16
Previous/concomitant meds ^c	X	X	X	X	X	X	X	X	X	X	X	X	X	X	X	X	X
Adverse events	X	X	X	X	X	X	X	X	X	X	X	X	X	X	X	X	X
Psychiatric and mental status		X			X			X			X						X
Urine drug screen/breath alcohol screen ^{b,c}		X			X			X			X						X
Pregnancy test ^d		X			X			X			X						X
Brief physical examination ^c		X			X			X			X						
Hem/chem/urine ^c	X							X									X

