Supine Vital signs (BP, RR, HR, T) ^e		X			X			X			X						
Triplicate 12-lead ECG ^e		X			X			X			X						
C-SSRS ^f		X															
CBD administration ^g		X	X	X	X	X	X	X	X	X	X	X	X	X	X	X	X
CBD PK trough sampling ^c		X			X			X			X						X
NeuroCart ^h	X																X
Arrival at the clinic		X			X			X			X						X

AE=adverse event; BID=twice daily; BP=blood pressure; CBD=cannabidiol; C-SSRS=Columbia-Suicide Severity Rating Scale; D=Day; ECG=electrocardiogram; h=hour; HR=heart rate; PK=pharmacokinetic; PSL=Padsevonil; RR=respiratory rate; SEM=Saccadic Eye Movements; T=body temperature; VAS=Visual Analog Scale; W=Week

-
- ^a A washout of at least 6 days will occur prior to the start of Treatment Period 3.
- ^b Performed at the discretion of the PI.
- ^c Prior to morning CBD administration.
- ^d Urine beta HCG will be collected either on the first day of the treatment period or the day before the first day of the treatment period at discretion of Investigator. In either case, the result must be negative prior to dosing study participants.
- ^e Prior to and 2.5 hours after morning CBD administration.
- ^f “Since Last Visit” version of the C-SSRS will be completed.
- ^g Days 1 to 3: CBD 2.5mg/kg BID; Days 4 to 6: CBD 5mg/kg BID; Days 7 to 9: CBD 7.5mg/kg BID; Days 10 to 16: CBD 10mg/kg BID (doses to be confirmed from CBD PK exposure in Treatment Period 1).
- ^h NeuroCart assessments in Part B consist of the following tests: Body Sway, VAS mood & alertness (Bond & Lader), VAS feeling high, internal- and external perception (Bowdle), SEM, and Smooth Pursuit Eye Movements. NeuroCarts assessments are taken twice at least 30 minutes prior to dosing and singlicate postdose at 30 minutes, 1, 2, 3, 4, 5, 6, 8, and 10 hours.

Table 1-8: Assessment schedule Part B: Treatment Period 4 and 5

Study Period	Treatment Periods 4 & 5						
Study day	D1	D2	D3	D4	D5	D6	D7
Previous/concomitant med ^a	X	X	X	X	X	X	X
Adverse events	X	X	X	X	X	X	X
Psychiatric and mental status	X	X	X	X	X	X	X
Brief physical examination ^a	X	X	X	X	X	X	X
Supine vital signs (BP, RR, HR, T) ^b	X	X	X	X	X	X	X
CBD 10 mg/kg BID ^c	X	X	X	X	X	X	X
PSL/placebo administration ^d	X	X	X	X	X	X	X
CBD PK trough sampling ^e	X	X	X	X	X	X	X
PSL PK trough sampling ^f	X	X	X	X	X	X	X
Triplicate 12-lead ECG ^b	X			X	X	X	X
C-SSRS ^g	X						X
NeuroCart ^h	X				X		
Start/stop urine collection ⁱ					X		
Hem/chem/urine ^a							X

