AE=adverse event; BID=twice daily; BP=blood pressure; CBD=cannabidiol; C-SSRS=Columbia-Suicide Severity Rating Scale; D=Day; ECG=electrocardiogram; h=hour; HR=heart rate; PK=pharmacokinetic; PSL=Padsevonil; RR=respiratory rate; SEM=Saccadic Eye Movements; T=body temperature; VAS=Visual Analog Scale

Note: A washout of at least 4 days will occur between Treatment Periods 4 and 5 for PSL.

^a Prior to PSL/placebo/CBD administration.

^b Prior to and 2.5 hours after IMP administration.

^c CBD maintenance 10mg/kg BID (dose to be confirmed from CBD PK exposure in Treatment Period 1) between Treatment Period 4 and Treatment Period 5 for 4 Days (study participants in house).

^d D1: PSL 100mg BID; D2: PSL 200mg BID; D3: PSL 200mg BID; D4: PSL 200mg BID; D5: PSL 200mg AM; D5: PSL 100mg PM; D6: PSL 100mg BID; D7: PSL 100mg BID.

-
- ^f Blood samples for measurement of plasma concentration of PSL and CBD will be obtained at the following times: predose (within 5 minutes of dosing), and at Day 5 (PK day) postdose at 0.25h, 0.5h, 1h, 1.5h, 2h, 3h, 4h, 6h, 8h, and 12h postdose.
- ^g “Since Last Visit” version of the C-SSRS will be completed.
- ^h NeuroCart assessments in Part B consist of the following tests: Body Sway, VAS mood & alertness (Bond & Lader), VAS feeling high, internal- and external perception (Bowdle), SEM, and Smooth Pursuit Eye Movements. NeuroCarts assessments are taken twice at least 30 minutes prior to dosing and singlicate postdose at 30 minutes, 1, 2, 3, 4, 5, 6, 8, and 10 hours.
- ⁱ Urine samples for additional PK analysis will be collected 12-hours postdose on Day 5.

Table 1-9: Assessment schedule Part B: Treatment Period 6 and SFU

Study Period	Treatment Period 6						SFU Visit ^a
	D1	D2	D3	D4	D5	D6/D7	
Adverse events	X	X	X	X	X	X	X
Previous/concomitant meds	X	X	X	X	X	X	X
Hem/chem/urine ^b						X	X
Supine vital signs (BP, RR, HR, T) ^c	X		X			X ^d	X
Psychiatric and mental status	X		X			X	X
Triplicate 12-lead ECG ^c	X		X			X ^d	X
C-SSRS ^e	X					X ^d	X
CBD administration ^f	X	X		X	X	X	
CBD PK trough sampling ^b	X		X			X	X
Physical examination ^g	X		X			X ^d	X
Pregnancy test						X ^h	
Discharge	X					X ^d	

AE=adverse event; BID=twice daily; BP=blood pressure; CBD=cannabidiol; C-SSRS=Columbia-Suicide Severity Rating Scale; D=Day; ECG=electrocardiogram; h=hour; HR=heart rate; PK=pharmacokinetic; PSL=Padsevonil; RR=respiratory rate; SAE=serious adverse event; T=body temperature; VAS=Visual Analog Scale; W=Week

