^a Study participants will return for a SFU Visit between 7 to 10 days after the final dose of CBD in Part B.

^b Prior to CBD administration.

^c Prior to and 2.5 hours after morning IMP administration.

^d Study participants will be discharged in the morning on Day 7 following the completion of all assessments.

^e “Since Last Visit” version of the C-SSRS will be completed.

^f Days 1 to 2: CBD 7.5mg/kg BID; Days 3 to 4: CBD 5mg/kg BID; Days 5 to 6: CBD 2.5mg/kg BID (doses to be confirmed from CBD PK exposure in Treatment Period 1).

^gBrief physical exams will be conducted during Part B Treatment Period 6. A full physical exam will be conducted at the SFU Visit.

^h For women of childbearing potential: Urine beta HCG will be performed.

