4.1.2 Part B

Treatment Period 1 of Part B will be conducted in a sentinel cohort of healthy study participants in order to evaluate CBD safety and PK exposure under a single dose of CBD 10mg/kg (fasted conditions). The results of the PK analysis will be compared to published PK data of CBD (dose of 750mg in fasted conditions) obtained in similar conditions with Epidiolex® (Taylor et al, 2018). The decision to continue on with the rest of Part B or terminate the study following the first CBD dose in Treatment Period 1 of Part B will be made pending the outcome of the analysis of CBD safety and exposure. A difference between the PK results in the present study and the literature findings requiring a >2-fold dose adjustment will be considered as not manageable and would result in termination of the study. If a dose adjustment \leq 2-fold is needed, then the study will proceed with the second dose of CBD of Treatment Period 1 in Part B. If the observed CBD exposure matches the data from the literature, then study will proceed directly to Treatment Period 2 of Part B (no second dosing of CBD will be required). Treatment Period 2 cannot commence until the results from Treatment Period 1 are analyzed.

A washout of at least 6 days will occur between Treatment Period 1 and Treatment Period 2. Treatment Period 2 will include 7 days of treatment with open-label PSL treatment. Treatment Period 3 starts after a washout of minimally 6 days for all study participants, and includes an ambulatory open-label CBD up titration of 16 days toward a maintenance level of 10mg/kg BID.

Treatment Periods 4 and 5 are 2-way cross-over, double-blind and placebo-controlled periods with PSL up titrated to a maintenance level of 200mg BID through Day 5 and subsequent down titration until Day 8. A maintenance dose of 10mg/kg BID CBD will occur in-house between Treatment Periods 4 and 5. Cannabidiol down titration starts in Treatment Period 6.

Study participants will be discharged at the end of Treatment Period 6 and return for a SFU Visit 7 to 10 days after the final dose of CBD. See Section 1.3.2 for the schedule of activities for Part B.

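### Part B requires a negative pregnancy test at the start of each treatment period, but none is scheduled for Treatment Period 5, which begins at least 12 days after the last test

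*Protocol*

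**What the plan says.** Footnote g of Protocol Table 1-5 sets the rule for women of childbearing potential in Part B: "urine beta HCG will be performed either on the first day of each treatment period" or on the preceding day. The investigator chooses between the two days. In either case a negative result is needed before dosing.

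The Part B schedules apply the rule as follows:

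- Table 1-6 (Treatment Period 2): test on Day -1.
- Table 1-7 (Treatment Period 3): tests on Days 1, 4, 7, 10 and 16.
- "Table 1-8: Assessment schedule Part B: Treatment Period 4 and 5": no pregnancy-test row. Its footnote letters a to i all belong to other listed rows.
- Table 1-9 (Treatment Period 6): one test at D6/D7, where footnote h reads "For women of childbearing potential: Urine beta HCG will be performed".

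Protocol Section 10.4.2.2 says that urine tests follow the schedule of activities. It adds unscheduled testing only when a cycle is missed or pregnancy is suspected.

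**The concern.** The footnote and the grid disagree about Treatment Period 5. The rule sits under the table for Screening and Treatment Period 1, while staff running Treatment Period 5 will have Table 1-8 in front of them. Protocol Section 8 treats adherence to the schedule as essential, so following the grid alone is a natural error.

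The omission matters most for sequence 2. Under the Part B sequence table in SAP Section 2.2.3, these participants take placebo with cannabidiol (CBD) in Treatment Period 4 and padsevonil (PSL) with CBD in Treatment Period 5, so they begin a new blinded PSL course there. Treatment Period 3 is described as an "ambulatory open-label CBD up titration of 16 days". A conception shortly before its Day 16 might be too early to show on that day's test. Confirmed pregnancy is a withdrawal criterion (Protocol Section 7.2, item 5), but a test that is not scheduled cannot trigger it.

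**Working it through.** **Inputs**

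- Interaction Phase days from SAP Table 3-3: Treatment Period 3 is days 1–16, Treatment Period 4 days 17–23, CBD maintenance days 24–27, Treatment Period 5 days 28–34, Treatment Period 6 days 35–41.
- The interval between Treatment Periods 4 and 5 is a minimum. The Table 1-8 note says "A washout of at least 4 days will occur between Treatment Periods 4 and 5 for PSL", and SAP Table 3-3 footnote c also gives at least 4 days of CBD maintenance.
- The washout before Treatment Period 3 is also a minimum: "A washout of at least 6 days will occur at the end of Treatment Period 2 prior to Treatment Period 3 in Part B" (Table 1-6 footnote b).
- PSL doses come from Table 1-8 footnote d.

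**Reproducing the plan's own figure.** Treatment Period 5 Day 1 = 16 + 7 + 4 + 1 = day 28, which matches SAP Table 3-3.

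**Intervals from the Day 16 test**

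| Interval | Calculation | Result |
|---|---|---|
| To Treatment Period 4 Day 1 | 17 − 16 | 1 day; rule met |
| To Treatment Period 5 Day 1 | 28 − 16 | at least 12 days; rule not met |
| To the next scheduled test (Treatment Period 6 D6) | 40 − 16 | at least 24 days |
| From the last Treatment Period 5 PSL day to that test | 40 − 34 | at least 6 days |

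Protocol Section 4.1.2 has down-titration in Treatment Periods 4 and 5 running to Day 8. If Treatment Period 4 lasts 8 days, the second interval becomes 13 days, so at least 12 still holds. Within Treatment Period 3 the longest gap between tests is 16 − 10 = 6 days.

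**PSL-free time in sequence 2.** The last PSL dose of Treatment Period 2 is on its Day 7. From then to Treatment Period 5 Day 1: 1 (PSL Phase day 8) + 6 (washout days 9–14) + 27 (Interaction Phase days 1–27) = 34 days, a minimum.

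**PSL given in Treatment Period 5.** Footnote d begins "D1: PSL 100mg BID; D2: PSL 200mg BID; D3: PSL 200mg BID; D4: PSL 200mg BID", followed by 200 mg and 100 mg on Day 5 and 100 mg twice daily on Days 6 and 7. The total is 200 + 400 + 400 + 400 + 300 + 200 + 200 = 2,100 mg, in 7 × 2 = 14 doses.

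**Women affected.** The documents do not give the number of women of childbearing potential. With 22 planned participants and equal allocation, sequence 2 has 22 / 2 = 11 people, so the range is 0 to about 11.

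**The case against.** **The test is already mandatory.** If footnote g reaches Treatment Period 5, all that is missing is a mark in a grid. If it is only a note to Table 1-5, there is no conflict, since Tables 1-6 and 1-7 carry their own footnotes. The wording of footnote g covers every treatment period, so the narrow reading is weak. The first half stands: harm needs a site to follow the grid and miss the footnote.

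**The tests may be meant for arrivals.** In Table 1-7 they fall exactly on the clinic-arrival days. In Table 1-6 the test is also on the arrival day, and participants are in house between Treatment Periods 4 and 5. The pattern is real, but neither document states such a rule, and it contradicts footnote g.

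**The rule is applied selectively.** Table 1-1 footnote e has the same wording for Part A, whose Table 1-3 (Treatment Periods 4 and 5) also has no test row; a literal reading reaches Part B Treatment Period 6 too. That is correct. The difference is in exposure: Part A PSL runs unbroken from Treatment Period 3, and Part B Treatment Period 6 only tapers CBD. Sequence 2 in Treatment Period 5 is a new start after a long break.

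**The chance of harm is very small.** This stands. Table 10-1 gives a failure rate below 1% a year for user-dependent methods used correctly. With 11 women and an assumed undetected window of 6 to 12 days, expected pregnancies are at most 11 × 0.01 × 6/365 = 0.002 to 11 × 0.01 × 12/365 = 0.004. A tenfold higher failure rate gives 0.02 to 0.04. If menses are assumed due 14 days after conception, a conception on days 10–15 gives a missed cycle around days 24–29. The missed-cycle safeguard would therefore act close to the start of Treatment Period 5, though not reliably before it. CBD exposure would already have occurred, and a Treatment Period 5 test could not avert it.

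**Conclusion.** The concern holds. The schedule contradicts the protocol's own rule for Part B Treatment Period 5, and no other section resolves it. The gap is at least 12 days from the last scheduled test, and the next one follows all Treatment Period 5 dosing by at least 6 days.

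This is a minor safety-schedule correction. It touches no endpoint, estimate, sample size or analysis. The benefit is confined to sequence 2, because sequence 1 has already taken PSL in Treatment Period 4 under the Day 16 test and CBD is continuous in both. The count of 0 to about 11 is of women without a scheduled test, not of expected pregnancies. The conclusion rests on reading footnote g as covering all Part B treatment periods and on the minimum intervals in SAP Table 3-3; longer intervals would widen the gap. The documents give no probability that the Day 16 test misses a very early pregnancy, and none is assumed here. The change is still worth making because it costs so little.

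**What to change.** Add a pregnancy-test row to Table 1-8, with a footnote: for women of childbearing potential, a urine beta-HCG on Treatment Period 5 Day 1 or the day before, negative before dosing. Apply it to both sequences, since testing only sequence 2 would reveal the allocation. No added test is needed at Treatment Period 4, which the Day 16 test covers, or at Treatment Period 6 Day 1, where only CBD is being reduced.

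The cost is one row, one footnote and one in-house urine test per woman of childbearing potential: 0 to 22 tests for the 22 planned participants. Footnote g already calls for these tests. With the row in place, the interval from test to Treatment Period 5 dosing falls from at least 12 days to 0 or 1 day.

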^a Refers to D-1 (Admission) prior to Part A Treatment Period 1 only.

^b A complete physical examination will be conducted at Part A Screening. A brief physical examination will be conducted at all other visits, including at discharge prior to the release of study participants.

^c Height measured only at Screening. Body weight will be measured at Part A Screening and predose in Part A Treatment Period 1 and 2.

^d All study participants will have a urine drug screen/breath alcohol test at admission. For study participants who are discharged between Treatment Periods, a urine drug screen/breath alcohol test will be performed at re-admission at the discretion of the PI.

^e For women of childbearing potential: A serum beta-HCG pregnancy test will be performed at Screening and urine beta HCG will be performed either on the first day of each treatment period or the day before the first day of each Treatment Period at discretion of Investigator. In either case, the results must be negative prior to dosing study participants.

^f Female study participants of non-childbearing potential to confirm postmenopausal status.

^g Virus serology (HIV-1/2Ab, HBsAg, and HCV-Ab) only at Screening.

^h Fasted conditions only at Screening.

ⁱ At the Screening Visit, “Baseline/Screening” version of the C-SSRS will be completed. At all other visits, “Since Last Visit” version of the C-SSRS will be completed.

^j In Part A Treatment Period 2 only.

^k Vital signs will be taken in a supine/standing position at Screening, and in a supine position at all other assessments.

^l PD training session for all study participants. Training session will be performed at the Screening visit or during a separate visit. Baseline PD assessment will be collected as a duplicate at D1 predose. Final Baseline score will be averaged (from duplicate values).

^m NeuroCart assessments in Part A consist of the following tests: Body Sway, VAS mood & alertness (Bond & Lader), VAS feeling high, internal- and external perception (Bowdle), SEM, Adaptive tracking, and Smooth Pursuit Eye Movements. NeuroCart assessments are taken twice at least 30 minutes prior to dosing and singlicate postdose at 30 minutes, 1, 2, 3, 4, 5, 6, 8, and 10 hours.

ⁿ Part A Treatment Period 1 only prior to ethanol dosing.

^o During the ethanol/dummy infusion, the infusion rate will be adjusted based on ethanol breath sampling.

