3 OBJECTIVES AND ENDPOINTS

The objectives and corresponding endpoints for this study are presented in [Table 3-1](#).

Table 3-1: Study objectives and endpoints

Objectives	Endpoints
Primary	

 Part A: To evaluate the PD interaction between steady-state treatment with PSL and ethanol 	
 Smooth pursuit (%) to assess eye movement coordination and attention

 Part B: To evaluate the PK interaction between steady-state treatment with PSL and CBD 	
 $C_{max,ss}$ and AUC_{τ} obtained from the plasma concentration-time profiles for PSL and CBD
Secondary	

 Part A: To evaluate the PK interaction between steady-state treatment with PSL and ethanol 	
 Ethanol dose infused over time $C_{max,ss}$ and AUC_{τ} obtained from the plasma concentration-time profiles for PSL

 Part B: To evaluate the PK interaction between steady-state treatment with PSL and CBD 	
 $t_{1/2}$, and $CL_{ss/F}$ obtained from the plasma concentration-time profiles for PSL and CBD

 Parts A and B: To evaluate the PD interaction between steady-state treatment with PSL and ethanol or between steady-state treatment with PSL and CBD 	
 Smooth pursuit (%) to assess eye movement coordination and attention (Part B only) Saccadic peak velocity (degrees/sec) to assess sedation Adaptive tracking (%) to assess visuo-motor control and vigilance Body Sway to assess postural stability

 Parts A and B: To evaluate the safety and tolerability of PSL in study participants receiving concomitant ethanol or CBD 	
 Adverse events (AEs), serious adverse events (SAEs), treatment-related AEs, and AEs leading to discontinuation of the study
Other	

 Parts A and B: To evaluate the safety and tolerability of PSL in study participants receiving concomitant ethanol or CBD 	
 Vital signs (pulse rate, respiratory rate, systolic blood pressure [SBP], and diastolic blood pressure [DBP]) 12-lead electrocardiogram (ECG) parameters Physical examination findings Clinical laboratory test results (hematology, clinical chemistry, and urinalysis)

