2.1.2 Part B

Objectives	Endpoints
Primary	
To evaluate the PK interaction between steady-state treatment with PSL and CBD	
 $C_{max,ss}$ and AUC_{τ} obtained from the plasma concentration-time profiles for PSL and CBD
Secondary	
To evaluate the PK interaction between steady-state treatment with PSL and CBD	
 $t_{1/2}$, and $CL_{ss/F}$ obtained from the plasma concentration-time profiles for PSL and CBD
To evaluate the PD interaction between steady-state treatment with PSL and CBD	
 Smooth pursuit (%) to assess eye movement coordination and attention

	
 • Saccadic peak velocity (degrees/sec) to assess sedation • Adaptive tracking (%) to assess visuo-motor control and vigilance • Body Sway to assess postural stability
To evaluate the safety and tolerability of PSL in study participants receiving concomitant CBD	
 • Adverse events (AEs), serious adverse events (SAEs), treatment-related AEs, and AEs leading to discontinuation of the study
Other	
To evaluate the safety and tolerability of PSL in study participants receiving concomitant CBD	
 • Vital signs (pulse rate, respiratory rate, systolic blood pressure [SBP], and diastolic blood pressure [DBP]) • 12-lead electrocardiogram (ECG) parameters • Physical examination findings • Clinical laboratory test results (hematology, clinical chemistry, and urinalysis)
To evaluate the PD interaction between steady-state treatment with PSL and CBD	
 • Visual analogue scales (VAS) Bond & Lader to assess study participant alertness, mood, and calmness • VAS feeling high, internal and external perception (Bowdle)
To evaluate the PK interaction between steady-state treatment with PSL and CBD	
 • t_{max} and C_{trough} obtained from the plasma concentration-time profiles for PSL and CBD • $C_{max,ss}$, AUC_{τ}, $t_{1/2}$, t_{max}, and metabolite/parent ratio (based on $C_{max,ss}$ and AUC_{τ}) obtained from the plasma concentration-time profiles for PSL metabolites and CBD active metabolite
To evaluate the plasma PK of single dose of CBD (Treatment Period 1)	
 • C_{max}, AUC_{0-t}, AUC, t_{max}, $t_{1/2}$ and CL/F

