10 PHARMACODYNAMICS

Pharmacodynamic parameters (absolute values and change from Baseline) will be summarized by phase, treatment, phase day and timepoint using the FAS. Figures of summaries and individual assessments will be based on the FAS.

The PD parameters include:

- Smooth Pursuit Eye Movements
- Body Sway
- VAS Mood and Alertness (Bond & Lader)
- VAS feeling high, internal and external perception (Bowdle)
- Saccadic eye movements
- Adaptive tracking
- VAS alcohol intoxication (Part A only)

For the derivation of VAS feeling high, internal and external perception (Bowdle) and VAS Mood and Alertness (Bond & Lader) see [Appendix 14.1](#) and [Appendix 14.2](#) respectively. The raw values of VAS alcohol intoxication will be presented, and any derivation required will be outlined in CSR.

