10.1.2.2 CBD and PSL (Part B)

The similarity of the PD parameters between treatment will be analyzed using the model specified in [Section 10.1.2](#), where treatment includes CBD, PSL, CBD+PSL and CBD+Placebo.

The following contrasts will be calculated within the model:

- CBD+PSL (Treatment Period 4/5: Day 5) vs PSL (Treatment Period 2: Day 5) (primary comparison)
- CBD+PSL (Treatment Period 4/5: Day 5) vs CBD (Treatment Period 3: Day 16)
- CBD+PSL (Treatment Period 4/5: Day 5) vs CBD+Placebo (Treatment Period 4/5: Day 5)

This analysis will also be performed for PD variables measured in Treatment Period 4/5, Day 1. Any treatment effect may be compounded by time in the first and second comparison stated above. Additionally, there may be a learning effect due to study participants performing the PD assessments multiple times.

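### Adaptive tracking is a Part B secondary endpoint, but every Part B NeuroCart definition leaves the test out, so following the schedule yields no data for it

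*Protocol*

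**What the plan says.** **Endpoint lists.** Protocol Section 1.1.4 and Table 3-1 set one secondary PD objective for both parts: "Parts A and B: To evaluate the PD interaction between steady-state treatment with PSL and ethanol or between steady-state treatment with PSL and CBD". Four endpoints sit under it: smooth pursuit, saccadic peak velocity, adaptive tracking and body sway. Smooth pursuit carries a part restriction, "Smooth pursuit (%) to assess eye movement coordination and attention (Part B only"), because it is already the Part A primary endpoint. Adaptive tracking carries none.

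SAP Section 2.1.2, which covers Part B alone, repeats "Adaptive tracking (%) to assess visuo-motor control and vigilance" as a secondary endpoint. The PD parameter list in SAP Section 10 includes adaptive tracking and limits only one item to a single part, "VAS alcohol intoxication (Part A only").

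**Part B schedule.** Table 1-8 footnote h (Treatment Periods 4 and 5) states "NeuroCart assessments in Part B consist of the following tests: Body Sway, VAS mood & alertness (Bond & Lader), VAS feeling high" and ends with "internal- and external perception (Bowdle), SEM, and Smooth Pursuit Eye Movements". Table 1-5 footnote l, Table 1-6 footnote j and Table 1-7 footnote h list the same tests.

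**Part A schedule.** Table 1-1 footnote m and Table 1-3 footnote g list the same tests plus adaptive tracking: "SEM, Adaptive tracking, and Smooth Pursuit Eye Movements".

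**The concern.** The endpoint lists and the SAP require a measurement that the Part B schedule never calls for. Site staff work from the schedule tables and their footnotes, and the Part B footnotes define the battery by a complete list rather than by examples. Taken literally, no Part B participant performs the test.

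At stake is the visuo-motor and vigilance endpoint of the padsevonil–cannabidiol interaction. SAP Section 10.1.2.2 plans to model the Part B PD parameters ("The similarity of the PD parameters between treatment will be analyzed using the model specified in" Section 10.1.2) and makes no exception for adaptive tracking. It specifies three contrasts, which draw on Day 5 of Treatment Period 2, Day 16 of Treatment Period 3 and Day 5 of Treatment Periods 4 and 5. It also plans the analysis for Day 1 of Treatment Periods 4 and 5. For adaptive tracking all of these would be empty. The measurements belong to specific on-treatment days, so the gap cannot be filled once a participant has completed those periods. Protocol Section 9.2 and SAP Section 4.2 rule out imputation.

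**Working it through.** No sample size, power or alpha figure is involved. The check compares each place that requires the endpoint with each place that could schedule it.

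| Place | Adaptive tracking in Part B? |
|---|---|
| Protocol 1.1.4 and Table 3-1, secondary | Yes; objective covers both parts, no restriction |
| SAP 2.1.2, secondary | Yes; table is for Part B only |
| SAP 10, PD parameter list | Yes; only the alcohol scale is limited to Part A |
| SAP 3.9, changes from the protocol | Not dropped |
| Table 1-5 footnote l (Screening, Period 1) | Absent |
| Table 1-6 footnote j (Period 2) | Absent |
| Table 1-7 footnote h (Period 3) | Absent |
| Table 1-8 footnote h (Periods 4 and 5) | Absent |
| Table 1-9 (Period 6, follow-up) | No NeuroCart row |
| Separate adaptive tracking row, Tables 1-5 to 1-9 | None |

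**Count.** The test appears in 0 of 4 Part B NeuroCart definitions and in 2 of 2 Part A definitions (Table 1-1 footnote m, Table 1-3 footnote g).

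**Text-extraction error.** This is an unlikely explanation. The Part B list is grammatically complete and appears in the same form four times, and the Part A sentence differs from it only by the added test.

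**Which text governs conduct.** Protocol Section 8 refers to the Schedule of Activities for procedures and their timing and treats adherence to it as essential. Section 8.7.6 describes how adaptive tracking is done but gives no visits or times, so it schedules nothing in either part.

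**Size.** Part B has four secondary PD endpoints, and one of them is not collected: 1/4. If the footnotes are followed, 0 of the 22 planned evaluable Part B participants contribute adaptive tracking data.

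**Burden if the test is added.** On a full NeuroCart day, Tables 1-6 to 1-8 require two predose sessions and nine postdose sessions (30 minutes, then 1, 2, 3, 4, 5, 6, 8 and 10 hours), which is 2 + 9 = 11. Section 8.7.6 gives 3.5 minutes of scored performance per test, so the added scored time is 11 × 3.5 = 38.5 minutes per day, plus a run-in of unstated length before each test. On Day 5 of Periods 2, 4 and 5, seven of the nine postdose sessions (0.5, 1, 2, 3, 4, 6 and 8 hours) coincide with pharmacokinetic draws.

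**The case against.** The strongest counter-argument is that other protocol text could lead the site to run the test anyway. Section 8.7 requires training on each PD assessment, Section 8.7.6 is not limited to Part A, and the study is run at one centre that performs the test for Part A. This makes the loss conditional on the footnotes being followed. It does not remove the conflict, because neither section sets a Part B time point. Section 8.6 allows timing changes and extra time points for planned assessments without an amendment, but that does not put an omitted test into the battery.

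A second argument is that the shorter Part B battery was intended and the shared endpoint row was simply not trimmed. The documents do not settle this. The four identical, Part B-specific footnotes favour that reading, while the separate Part B endpoint table in the SAP points the other way. If the omission was deliberate, no intended data are lost and the error lies in the endpoint wording, but the two sets of text still need reconciling.

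Third, the impact is bounded, and this point stands. The Part B primary objective is pharmacokinetic. The PD results are reported as contrasts with 95% confidence intervals, without a stated decision rule. Sedation, attention and self-rated alertness are still measured through saccadic peak velocity, smooth pursuit and the Bond and Lader scales. None of these replaces a visuo-motor tracking task, but the wider PD objective survives.

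**Conclusion.** The concern holds. Adaptive tracking is a required Part B secondary endpoint in both documents, and no Part B schedule table collects it. If the site follows the schedule as written, 0 of 22 participants have data and 1 of 4 Part B secondary PD endpoints cannot be analysed.

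This rests on one assumption: that the footnotes define what is actually done, which Section 8 supports. It does not depend on which text reflects the sponsor's intention, since one of the two is wrong in either case. This is an internal inconsistency that should be corrected. It does not threaten the Part B primary analysis or the sample size.

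**What to change.** Decide before Part B PD collection which text is intended, then change one set of passages.

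- **If the endpoint is wanted in Part B:** add adaptive tracking to Table 1-6 footnote j, Table 1-7 footnote h and Table 1-8 footnote h, which cover the days used in the SAP contrasts. Add it also to Table 1-5 footnote l so that the battery is uniform and the training session at Screening includes it. No SAP contrast uses Treatment Period 1, so Table 1-5 matters mainly for training. The cost is footnote wording plus the 3.5-minute test and its run-in at each existing session. The order of tests needs checking against the Day 5 blood draws. No new equipment should be needed if the Part A set-up at the same centre can be used, but the documents do not confirm this.
- **If the shorter battery is intended:** mark adaptive tracking as Part A only in protocol Section 1.1.4 and Table 3-1, remove it from SAP Section 2.1.2, and mark it as Part A only in SAP Section 10. The cost is wording alone.

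If Part B measurements have already been taken without the test, SAP Section 3.9 should state that the endpoint was not collected in Part B and will not be analysed there.
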